## 7.2 Adverse Event Characteristics

*For expedited reporting purposes only*

1. AEs for the agent that are ***bold and italicized*** in the CAEPR (*i.e.*, those listed in the SPEER column, [Section 7.1](#)) should be reported through CTEP-AERS only if the grade is above the grade provided in the SPEER.
2. Other AEs for the protocol that do not require expedited reporting are outlined in [Section 7.3](#)

*Attribution of the AE*

1. Definite – The AE is clearly related to the study treatment.
2. Probable – The AE is likely related to the study treatment.
3. Possible – The AE may be related to the study treatment.
4. Unlikely – The AE is doubtfully related to the study treatment.
5. Unrelated – The AE is clearly NOT related to the study treatment.

## 7.3 Expedited Adverse Event Reporting

7.3.1 Expedited AE reporting for this study must use CTEP AERS (Adverse Event Expedited Reporting System), accessed via the CTEP Web site (<http://ctep.cancer.gov>). The reporting procedures to be followed are presented in the “NCI Guidelines for Investigators: Adverse Event Reporting Requirements for DCTD (CTEP and CIP) and DCP INDs and IDEs” which can be downloaded from the CTEP Web site (<http://ctep.cancer.gov>). These requirements are briefly outlined in the tables below ([Section 7.3.3](#)).

In the rare occurrence when Internet connectivity is lost, a 24-hour notification is to be made to CTEP by telephone at [contact]. Once Internet connectivity is restored, the 24-hour notification phoned in must be entered electronically into CTEP-AERS by the original submitter at the site.

7.3.2 CTEP-AERS is programmed for automatic electronic distribution of reports to the following individuals: Study Coordinator of the Lead Organization, Principal Investigator, and the local treating physician. CTEP-AERS provides a copy feature for other e-mail recipients.

### 7.3.3 Expedited reporting guidelines

Use the NCI protocol number and the protocol-specific participant ID assigned during trial registration on all reports.

**Note: A death on study requires both routine and expedited reporting regardless of causality, unless as noted below. Attribution to treatment or other cause must be provided.**

Death due to progressive disease should be reported as **Grade 5 “General disorders and administration site conditions - Disease Progression.”** Evidence that the death was a manifestation of underlying disease (e.g., radiological changes suggesting tumor growth or progression; clinical deterioration associated with a disease process) should be submitted.

**Phase I Studies: Expedited Reporting Requirements for Adverse Events that Occur on Studies under an IND/IDE within 30 Days of the Last Administration of the Investigational Agent/Intervention **

**FDA REPORTING REQUIREMENTS FOR SERIOUS ADVERSE EVENTS (21 CFR Part 312)**

**NOTE:** Investigators **MUST** immediately report to the sponsor (NCI) **ANY** Serious Adverse Events, whether or not they are considered related to the investigational agent(s)/intervention (21 CFR 312.64)

An adverse event is considered serious if it results in **ANY** of the following outcomes:

- 1) Death
- 2) A life-threatening adverse event
- 3) An adverse event that results in inpatient hospitalization or prolongation of existing hospitalization for  $\geq 24$  hours
- 4) A persistent or significant incapacity or substantial disruption of the ability to conduct normal life functions
- 5) A congenital anomaly/birth defect.
- 6) Important Medical Events (IME) that may not result in death, be life threatening, or require hospitalization may be considered serious when, based upon medical judgment, they may jeopardize the patient or subject and may require medical or surgical intervention to prevent one of the outcomes listed in this definition. (FDA, 21 CFR 312.32; ICH E2A and ICH E6).

**ALL SERIOUS** adverse events that meet the above criteria **MUST** be immediately reported to the NCI via CTEP-AERS within the timeframes detailed in the table below.

Hospitalization	Grade 1 and Grade 2 Timeframes	Grade 3-5 Timeframes
Resulting in Hospitalization $\geq 24$ hrs	10 Calendar Days	24-Hour 5 Calendar Days
Not resulting in Hospitalization $\geq 24$ hrs	Not required	

**NOTE:** Protocol specific exceptions to expedited reporting of serious adverse events are found in the Specific Protocol Exceptions to Expedited Reporting (SPEER) portion of the CAEPR.

**Expedited AE reporting timelines are defined as:**

- “24-Hour; 5 Calendar Days” - The AE must initially be reported via CTEP-AERS within 24 hours of learning of the AE, followed by a complete expedited report within 5 calendar days of the initial 24-hour report.
- “10 Calendar Days” - A complete expedited report on the AE must be submitted within 10 calendar days of

learning of the AE.

Serious adverse events that occur more than 30 days after the last administration of investigational agent/intervention and have an attribution of possible, probable, or definite require reporting as follows:

**Expedited 24-hour notification followed by complete report within 5 calendar days for:**

- All Grade 3, 4, and Grade 5 AEs

**Expedited 10 calendar day reports for:**

- Grade 2 AEs resulting in hospitalization or prolongation of hospitalization

For studies using PET or SPECT IND agents, the AE reporting period is limited to 10 radioactive half-lives, rounded UP to the nearest whole day, after the agent/intervention was last administered. Footnote “1” above applies after this reporting period.

Effective Date: May 5, 2011

## 7.4 Routine Adverse Event Reporting

All Adverse Events must be reported in routine study data submissions. AEs reported through CTEP-AERS must also be reported in routine study data submissions.

## 7.5 Secondary Malignancy

A *secondary malignancy* is a cancer caused by treatment for a previous malignancy (e.g., treatment with investigational agent/intervention, radiation, or chemotherapy). A secondary malignancy is not considered a metastasis of the initial neoplasm.

CTEP requires all secondary malignancies that occur following treatment with an agent under an NCI IND/IDE be reported via CTEP-AERS. Three options are available to describe the event:

1. Leukemia secondary to oncology chemotherapy (e.g., acute myelocytic leukemia [AML])
2. Myelodysplastic syndrome (MDS)
3. Treatment-related secondary malignancy

Any malignancy possibly related to cancer treatment (including AML/MDS) should also be reported via the routine reporting mechanisms outlined in each protocol.

## 7.6 Second Malignancy

A second malignancy is one unrelated to the treatment of a prior malignancy (and is **NOT** a metastasis from the initial malignancy). Second malignancies require **ONLY** routine reporting via CDUS unless otherwise specified.

## 8.0 PHARMACEUTICAL INFORMATION

A list of the adverse events and potential risks associated with the investigational agent administered in this study can be found in [Section 7.1](#).

### 8.1 CTEP IND Agent

#### 8.1.1 Cabozantinib (XL184) (NSC 761968)

**Chemical Name:** *N*-{4-[(6,7-dimethoxyquinolin-4-yl)oxy]phenyl}-*N'*-(4-fluorophenyl)cyclopropane-1,1-dicarboxamide, (2S)-hydroxybutanedioate

**Other Names:** Cabozantinib, EXEL-7184, EXEL-02977184

**Classification:** Receptor Tyrosine Kinases Inhibitor (RTK)

**CAS Registry Number:** 1140909-48-3

**Molecular Formula:** C28H24FN3O5.C4H6O5      **M.W.:** 635.6

**Mode of Action:** Cabozantinib inhibits multiple RTKs implicated in tumor growth, metastasis, and angiogenesis, and targets primarily MET and VEGFR2. Other targets are RET, AXL, KIT, TIE-2, and FLT-3.

**How Supplied:** Cabozantinib is supplied by Exelixis and distributed by the DCTD. Cabozantinib is available in 20 mg and 60 mg tablets. The tablets are yellow film coated containing cabozantinib malate equivalent to 20 mg and 60 mg of cabozantinib. The 20 mg tablets have a round shape and the 60 mg tablets have an oval shape, and they are packaged as 30 tablets per bottle.

Cabozantinib should be dispensed in its original container; however, for treatment duration for up to a week, cabozantinib tablets can be dispensed in a pill cup with an expiration date not to exceed 24 hours or in a pharmacy dispensing bottle with expiration date not to exceed 7 days.

#### Cabozantinib (XL184) Tablet Components and Composition

Ingredient	Function	% w/w
Cabozantinib malate (25% drug load as cabozantinib)	Active Ingredient	31.7
Microcrystalline Cellulose (Avicel PH-102)	Filler	38.9
Lactose Anhydrous (60M)	Filler	19.4
Hydroxypropyl Cellulose (EXF)	Binder	3.0
Croscarmellose Sodium (Ac-Di-Sol)	Disenegrant	6.0
Colloidal Silicon Dioxide,	Glidant	0.3
Magnesium Stearate	Lubricant	0.75
Opadry Yellow Film Coating which includes:		
- HPMC 2910 / Hypromellose 6 cp		
- Titanium dioxide	Film Coating	4.00
- Triacetin		
- Iron Oxide Yellow		

**Storage:** Store intact bottles at controlled room temperature, 20^0 to 25C.

**Stability:** Stability testing of the intact bottles is on-going. Cabozantinib is stable up to 24 hours when dispensed in an open container such as a pill cup, and up to 7 days when dispensed in a closed container such as a pharmacy bottle other than the original container.

**Route of Administration:** Oral.

**Method of Administration:** *Take cabozantinib on an empty stomach. Participants must fast for 2 hours before and 1 hour after each dose of cabozantinib. Do not crush or chew. Do not take missed dose within 12 hours of the next dose.*

**Potential Drug Interactions:**

**CYP450 isozymes**

*In vitro*, XL184 is a substrate of CYP3A4 and a weak substrate of CYP2C9. In healthy volunteers, XL184 AUC increased 38% with co-administration of ketoconazole, a strong inhibitor of CYP3A4, and decreased by 77% with a strong CYP3A4 inducer rifampin. Therefore, avoid chronic use of strong CYP3A4 inducers such as rifampin, dexamethasone, phenytoin, carbamazepine, rifabutin, rifampentin, phenobarbital, and St. John's Wort while taking XL184. Avoid chronic use of strong CYP3A4 inhibitors such as ketoconazole, itraconazole, clarithromycin, indinavir, nefazodone, nelfinavir, and ritonavir. Use alternative medications. **Use of antiretroviral agents that are strong inducers or inhibitors of CYP3A4 are permitted as per exclusion criteria 3.2.10 and 3.2.11.**

[Note: Use caution when discontinuing medication that is a strong inducer of CYP3A4 in patients who has been on a stable dose of XL184, as this could significantly increase the exposure to XL184.]

XL184 is a noncompetitive inhibitor of CYP2C8 ( $K_{iapp} = 4.6 \mu M$ ), a mixed-type inhibitor of both CYP2C9 ( $K_{iapp} = 10.4 \mu M$ ) and CYP2C19 ( $K_{iapp} = 28.8 \mu M$ ), and a weak competitive inhibitor of CYP3A4 (estimated  $K_{iapp} = 282 \mu M$ ) in human liver microsomal (HLM).  $IC_{50}$  values  $>20 \mu M$  were observed for CYP1A2, CYP2D6, and CYP3A4 isozymes. XL184 is an inducer of CYP1A1 mRNA in human hepatocyte incubations,

Avoid grapefruit/ grapefruit juice and Seville oranges while participating in this trial.

**P-glycoprotein/ MRP2**

*In vitro* data indicate that XL184 is an inhibitor of P-glycoprotein transport activity ( $IC_{50} = 7.0 \mu M$ ). Co-administration of XL184 with a P-gp substrate may result in an increase in P-gp substrate plasma concentration. Therefore, use caution when administering XL184 with drugs known to be P-gp substrates (e.g., fexofenadine, aliskiren, ambrisentan, digoxin, colchicine, maraviroc, posaconazole, tolvaptan, etc.).

XL184 is also a substrate of drug transporter MRP2, which may result in an increase plasma concentration of XL184 when administered with an inhibitor of MRP2. Use caution and monitor adverse events when administering XL184 with MRP2 inhibitors such as cyclosporine, delavirdine, efavirenz, emtricitabine.

#### Protein bound

XL184 is highly protein bound ( $\geq 99.9\%$ ). Use caution when coadministering XL184 with medications that are highly protein-bound (e.g., diazepam, furosemide, dicloxacillin, and propranolol). Avoid administration of warfarin with XL184 as warfarin is highly protein-bound and has a very narrow therapeutic index.

#### Antacids, H2-blockers, PPIs

Co-administration of gastric pH modifying drugs such as PPI, H2-blockers or antacids has no clinically-relevant effect on XL184 plasma PK in healthy volunteers; thus, concomitant use of these drugs with XL184 is allowed.

#### QTc prolongation

Use caution when administering XL184 in patients with QT prolongation risk, a history of QT interval prolongation, or who are receiving antiarrhythmic drugs. Concomitant use of strong CYP3A4 inhibitors should be avoided as it may increase XL184 plasma concentrations. Refer to the protocol for QTcF criteria.

#### **Potential Food Effect**

A high fat meal increased both XL184 Cmax and AUC values by 41% and 57%, respectively relative to fasted conditions; therefore, XL184 should be taken on an empty stomach (fasting is required 2 hours before and 1 hour after each XL184 dose).

**Participant Care Implications:** Do not take grapefruit/ grapefruit juice or Seville oranges while participating in this trial. Inform physician and study healthcare team about current medications including over the counter drugs, herbals, or natural medicines. Refer to the protocol for management of adverse events.

**Availability:** Cabozantinib (XL184) is an investigational agent supplied to investigators by the Division of Cancer Treatment and Diagnosis (DCTD), NCI.

Cabozantinib (XL184) is provided to the NCI under a Collaborative Agreement between the Pharmaceutical Collaborator and the DCTD, NCI (see [Section 12.3](#)).

#### 8.1.2 Agent ordering and agent accountability

8.1.2.1 NCI-supplied agents may be requested by the Principal Investigator (or their authorized designee) at each participating institution. Pharmaceutical Management Branch (PMB) policy requires that agent be shipped directly to the institution where the patient is to be treated. PMB does not permit the transfer of agents between institutions (unless prior approval from PMB is obtained). The CTEP-assigned protocol number must be used for ordering all CTEP-supplied investigational agents. The responsible investigator at each participating institution must be registered with CTEP,

DCTD through an annual submission of FDA Form 1572 (Statement of Investigator), Curriculum Vitae, Supplemental Investigator Data Form (IDF), and Financial Disclosure Form (FDF). If there are several participating investigators at one institution, CTEP-supplied investigational agents for the study should be ordered under the name of one lead investigator at that institution.

Active CTEP-registered investigators and investigator-designated shipping designees and ordering designees can submit agent requests through the PMB Online Agent Order Processing (OAOP) application (<https://eapps-ctep.nci.nih.gov/OAOP/pages/login.jspx>). Access to OAOP requires the establishment of a CTEP Identity and Access Management (IAM) account (<https://eapps-ctep.nci.nih.gov/iam/>) and the maintenance of an “active” account status and a “current” password. For questions about drug orders, transfers, returns, or accountability, call [contact] Monday through Friday between 8:30 am and 4:30 pm (ET) or email [[contact]](mailto:[contact]) anytime.

8.1.2.2 Agent inventory records - The investigator, or a responsible party designated by the investigator, must maintain a careful record of the inventory and disposition of all agents received from DCTD using the NCI Investigational Drug Accountability Record Form for Oral Agents (Oral DARF). (See the NCI Investigator’s Handbook for Procedures for Drug Accountability and Storage.). The Oral DARFs document the drug delivery date to the site, inventory at the site, use by each study participant, and disposal of the drug (if applicable). The Oral DARF is also used to document agent returned by the participant. A site-specific accountability record, either manual or electronic, may be used if it includes all of the information required on the Oral DARF and if the paper printout is identical to the NCI accountability record. A separate Oral DARF is required for each protocol using the same agent. The investigator will ensure that the drugs are used only in accordance with this protocol.

8.1.2.3 Dispensing agent – Pharmacy staff should dispense cabozantinib in its original container. The pharmacist may dispense the entire intact bottle, a pill cup not to exceed 24 hours of medication, or another pharmacy dispensing bottle not to exceed 7 days’ worth of medication. If an entire intact bottle is dispensed all agents must be returned at the end of the cycle and unused agent destroyed. The site staff is responsible for ensuring all unused agent is returned and destroyed.

8.1.2.4 Returns of unused agent - study participants are required to complete the participant drug diary and to return all remaining agent and/or empty bottles at the end of each cycle of treatment. Site staff will be responsible for documenting pill counts at the end of each cycle. The pill count will be used to evaluate the information reported in the participant drug diary.

## **9.0 CLINICAL AND LABORATORY EVALUATIONS**

Schedule of Evaluations is provided in [Appendix I](#).

### **9.1 Screening/Baseline Evaluations**

Unless otherwise specified, the following evaluations must be performed within 1 week prior to start of therapy:

- 9.1.1 Complete medical history and physical examination, to include concurrent medications, medication history for eligibility (including ART regimen for 4 weeks prior to enrollment), vital signs, height, weight, performance status, CDC HIV risk categories, and history of AIDS defining conditions.
- 9.1.2 AIDS and Cancer Specimen Resource (ACSR) Consent for optional donation. It is required that AMC sites present the ACSR donation option to participants. (See [Appendix VII](#) for ACSR Informed Consent Form and [Appendix VI](#) for ACSR Specimen Preparation and Shipping Instructions).
- 9.1.3 CBC with differential and platelets, Serum chemistry: albumin, bicarbonate, BUN, calcium, chloride, creatinine, glucose, LDH, phosphorus, potassium, sodium, total protein and magnesium; Liver function tests: albumin, SGOT [AST], SGPT [ALT], total bilirubin, alkaline phosphatase.
- 9.1.4 Serum TSH, amylase, lipase
- 9.1.5 PT/INR and PTT
- 9.1.6 CD4+ and CD8+ lymphocyte counts and HIV viral load within 2 weeks prior to the start of therapy
- 9.1.7 Serum pregnancy test (for women of childbearing potential)
- 9.1.8 Urine dipstick or urinalysis. Proteinuria seen on urine dipstick or UA should warrant urine protein/creatinine ratio (UPCR) determination and management according to [Section 6.1.9](#).
- 9.1.9 Electrocardiogram (ECG) and QTc assessments within 4 weeks prior to the start of therapy.
- 9.1.10 CT scans to evaluate measurable disease within 4 weeks of start of therapy. CT will not be required for participants with KS.
- 9.1.11 ONLY in participants with known Kaposi sarcoma, chest X-ray to rule out pulmonary Kaposi's sarcoma. Pulmonary involvement must be asymptomatic or minimally symptomatic and not require systemic cytotoxic therapy in the judgment of the investigator. Participants with a positive chest X-ray or symptoms suggestive of pulmonary disease must have a chest CT performed before study entry.

### **9.2 Evaluations During Treatment**

Evaluations may occur within a window of +/- 7 days. Assessments must occur on cycle 1, days 1, 8, 15, and 22, on Cycle 2, days 1 and 15, and on day 1 of all subsequent cycles as indicated in the Schedule of Evaluations ([Appendix I](#)).

- 9.2.1 Complete medical history and physical examination. To include vital signs, weight, performance status, adverse event evaluation). If hypertension (BP 140/90) is observed, decisions to decrease or hold the dose of study treatment must be based on BP readings taken by a medical professional and must be confirmed with a second measurement at least 5 minutes following the first measurement. (Refer to [Section 6.1.8](#) for management.)
- 9.2.2 CBC with differential and platelets, serum chemistry, amylase and lipase, and LFTs defined in [9.1.3](#).
- 9.2.3 Serum TSH. Testing should be performed every 4 weeks (every cycle) beginning Cycle 1 Day 1.
- 9.2.4 PT/INR and PTT. Testing should be performed every 8 weeks (2 cycles) beginning Cycle 1 Day 1.
- 9.2.5 CD4+ and CD8+ lymphocyte counts and HIV viral load. Samples will be obtained locally at time of Pharmacokinetic (PK) Specimen Collection on Cycle 1, Day 22, and at 12 week intervals while on study therapy.
- 9.2.6 Urine dipstick or urinalysis. Proteinuria seen on urine dipstick or UA should warrant urine protein/creatinine ratio (UPCR) determination and management according to [Section 6.1.9](#).
- 9.2.7 ECG and QTc assessments will be performed weekly during the first cycle of therapy, and day 1 of all subsequent cycles. Additional ECGs will be performed as indicated in [Section 6.1.16](#) (refer to [Appendix IX](#) for a list of drugs that may cause QTc prolongation).
- 9.2.8 CT scan for tumor measurement performed after every 2 cycles (every 8 weeks) of therapy for participants with solid tumors. Participants with cutaneous KS will not require CT scans.
- 9.2.9 KS participants will be evaluated for response after every other cycle according to the requirements in [Section 11.2](#). Chest x-ray will be performed as clinically indicated.
- 9.2.10 The participant will be given a copy of the participant diary to complete. Collect diary upon completion.
- 9.2.11 Correlative Studies (See [Section 10.0](#))

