### 5.2 Definition of Dose-Limiting Toxicity

Dose escalation decisions for cabozantinib will be made after evaluation of toxicities in the first cycle of therapy. In this trial, a dose-limiting toxicity (DLT) will be defined as any cabozantinib-related grade 3 or 4 non-hematologic toxicity during the first cycle of therapy, including grade 3 nausea and/or vomiting and grade 3 diarrhea despite prophylaxis and/or treatment or any of the following grade 4 hematologic toxicities during the first cycle of therapy: thrombocytopenia and neutropenia of any duration (with or without fever or documented infection); additionally, treatment delay of greater than 7 days during Cycle 1 due to unresolved toxicity or any dose reduction required during Cycle 1 due to a cabozantinib-related adverse event (including for intolerable cabozantinib-related grade 2 non-hematological toxicity – per Table 6-1) will be considered a DLT.

For all participants who experience a DLT or other persistent and severe toxicity, a blood sample for pharmacokinetics analysis will be requested from the participant (if feasible). The samples should be drawn as close as possible to the time of the event.

If a DLT occurs in one participant at a particular dose level, up to 3 additional participants will be added to that cohort. If a second participant experiences a DLT, the maximally tolerated dose (MTD) of the study will have been exceeded. If 2 DLTs are experienced at the first cohort, one dose level de-escalation (Dose Level -1) will be permitted according to the study schema suggested in the treatment plan.

Management and dose modifications associated with the above adverse events are outlined in [Section 6.0](#).

Dose escalation will proceed in participant cohorts within each Stratum ([Section 5.1](#)) according to the following scheme. Participants are considered evaluable for the purpose of cohort dose escalations if in the first cycle they either experience a DLT (defined above), or receive at least 80% of the planned treatment dose and are followed for one full cycle without a DLT. Participants receiving less than 80% of the treatment dose during cycle 1 without a DLT may be replaced for the purpose of safety and PK evaluation at the discretion of the study team.

Number of Participants with DLT at a Given Dose Level	Escalation Decision Rule
0 out of 3	Enter 3 participants at the next dose level.

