### 10.2.1.1 Collection of specimens

This study will be performed on all participating participants as described in [Appendix IV](#), Pharmacokinetic (PK) Specimen Collection, Preparation and Shipping Instructions. Samples will be collected prior to the initial cabozantinib dose and at 4 hours post-dose on Cycle 1 Day 1. Steady-state PK samples will be collected during the dosing interval at pre-dose (Cycle 1, Day 22), 0.5, 1, 2, 4, 6, 8, and 24 hr (Cycle 1, Day 23). Day 22 and Day 23 PK samples may be collected  $\pm$  1 day. If a participant misses a dose of cabozantinib during Cycle 1 prior to Cycle 1 Days 22/23 and will continue on treatment, [name] should be contacted to determine the optimal timing of the PK collection, which may no longer occur on Cycle 1 Days 22/23. In addition, when feasible, samples will be requested from the participant at the time of disease progression and in the event of DLT or other persistent and severe toxicity.

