## APPENDIX I: SCHEDULE OF EVALUATIONS

The schedule of evaluations below applies to all participants on study. Baseline clinical and laboratory evaluations are to be conducted within 1 week prior to start of protocol therapy. Scans and x-rays must be done within 4 weeks prior to the start of therapy. In the event that the participant's condition is deteriorating, laboratory evaluations should be repeated within 48 hours prior to initiation of the next cycle of therapy. Evaluations may occur within a window of +/- 7 days. Assessments must occur on cycle 1, days 1, 8, 15, and 22, on Cycle 2, days 1 and 15, and on day 1 of all subsequent cycles.

	Pre-Study	C1/ D1	C1/ D8	C1/ D1 5	C1/ D22	C2/ D1	C2/ D8	C2/ D1 5	C2/ D22	C3/ D1	C4/ D1	C5/ D1	C6/ D1 k	Treatment Discontinuation p
Cabozantinib (XL184)		A				A				A	A	A	A	
Informed consent	X													
Demographics	X													
Medical history and Concurrent meds	X	X-----												X
Physical exam	X	X	X	X	X	X		X		X	X	X	X	X
Vital signs a	X	X	X	X	X	X		X		X	X	X	X	X
Height	X													
Weight	X	X	X	X	X	X		X		X	X	X	X	X
Performance status	X	X	X	X	X	X		X		X	X	X	X	X
CBC w/diff, plts, LFTs	X	X	X	X	X	X		X		X	X	X	X	X
Serum chemistry b	X c	X	X	X	X	X		X		X	X	X	X	X
Urine Dipstick or UA b	X	X	X	X	X	X		X		X	X	X	X	X
Serum TSH	X	X				X				X	X	X	X	X
Electrocardiogram (ECG) d	X o	X	X	X	X	X				X	X	X	X	X
Adverse event evaluation		X-----												X
Tumor measurements	X	Solid tumor measurements are repeated every 8 weeks (2 cycles). KS participants will be evaluated for response after every other cycle. Documentation (radiologic) must be provided for participants removed from study for progressive disease.												X
Radiologic evaluation	X l	Radiologic measurements should be performed every 8 weeks (2 cycles)												X
PT/INR, PTT	X	Repeat testing should be performed at 8 weeks (end of Cycle 2).												X

Amylase and Lipase	X e	X	X	X	X	X		X		X	X	X	X	X	
B-HCG	X e														
CD4+ and CD8+ Lymphocyte Counts and HIV Viral Load f	X n					X					X				X
ACSR donation	X g														
Cabozantinib diary h		X				X				X	X	X	X	X	
Pharmacokinetic (PK) sampling studies i		X i			X i										X j

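### The ±7-day window on Cycle 1 assessments equals their 7-day spacing, so safety labs may lie 14 to 21 days apart and some short, silent laboratory DLTs could be missed

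*Combined protocol and SAP*

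**What the plan says.** Section 9.2 puts two rules next to each other: "Evaluations may occur within a window of +/- 7 days. Assessments must occur on cycle 1, days 1, 8, 15, and 22". The introduction to Appendix I repeats the general allowance, "Evaluations may occur within a window of +/- 7 days", again with no exception for Cycle 1. The panels on these days are "CBC with differential and platelets, serum chemistry, amylase and lipase, and LFTs defined in" Section 9.1.3; the Appendix I table places them, with the urine test, at Cycle 1 Days 1, 8, 15 and 22 and Cycle 2 Day 1.

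Section 5.2 states that "Dose escalation decisions for cabozantinib will be made after evaluation of toxicities in the first cycle of therapy". A DLT includes "any cabozantinib-related grade 3 or 4 non-hematologic toxicity during the first cycle of therapy" and, at grade 4, "thrombocytopenia and neutropenia of any duration (with or without fever or documented infection"). Under Sections 5.2 and 12.1 a participant without a DLT is evaluable after 80% of the planned dose and a full cycle of follow-up. No number of laboratory panels is required.

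Tighter timing is given for other items only. Section 10.2.1.1 says "Day 22 and Day 23 PK samples may be collected" within one day either side, and Appendix IV lets the Study Chairs waive steady-state PK samples. Section 9.2.7 calls for weekly ECGs in Cycle 1.

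**The concern.** A visit window is meant to absorb scheduling slippage while keeping the visits distinct. Here the tolerance equals the spacing, so it can remove the spacing altogether. No text sets a minimum interval between panels, says that one draw cannot satisfy two scheduled days, or gives the Cycle 1 safety labs a narrower tolerance.

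A grade 4 cytopenia without fever, or a grade 3–4 enzyme or electrolyte change without symptoms, is found only by testing. If it comes and goes between widely spaced panels, the participant counts as DLT-free. The error runs one way: a level looks better tolerated than it is. That bears on escalation in Strata A and B. In Stratum C, which does not escalate, it bears on whether the starting level is judged tolerable.

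The background section shows that such events occur with this agent. In the Japanese phase I study (Section 2.4), two of the three subjects in the first cohort had DLTs of proteinuria and thrombocytopenia. In the rosiglitazone interaction study, grade 3 or higher events among 11 patients included hypophosphatemia (27%), raised amylase (9%) and hyponatremia (9%).

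**Working it through.** The plan states no figure for this, so there is none to reproduce.

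**1. Windows.** Nominal days 8, 15 and 22 with ±7 give Days 1–15, 8–22 and 15–29. Their only common day is Day 15.

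**2. Permitted gaps**, taking Cycle 2 Day 1 as Day 29:
- Nominal: panels on Days 1, 8, 15, 22, 29; longest gap 7 days.
- Pattern X, one draw on Day 15 for all three: panels on Days 1, 15, 29; gaps of 14 days.
- Pattern Y, Day 22 held by PK, the Day 1 panel taken as Day 8, and Day 15 labs drawn on Day 22: panels on Days 1, 22, 29; longest gap 22 − 1 = 21 days.

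**3. Detection.** Assume an abnormality lasting L days with onset equally likely on each of Days 2–28 (27 days). A panel on day t catches onsets from t − L + 1 to t. For L = 7:
- Nominal: 27/27 = 100%.
- X: Day 15 catches onsets 9–15 (7) and Day 29 catches 23–28 (6); 13/27 = 48%.
- Y: Day 22 catches onsets 16–22 (7) and Day 29 catches 23–28 (6); 13/27 = 48%.

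| Duration L | Nominal | X | Y |
|---|---|---|---|
| 5 days | 70% | 33% | 33% |
| 7 days | 100% | 48% | 48% |
| 10 days | 100% | 70% | 59% |
| 14 days | 100% | 100% | 74% |

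If Cycle 2 Day 1 also slips to Day 36, pattern X catches 26% of 7-day events.

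**4. Effect on the 3+3 rule.** A level is cleared on 0/3 DLTs, or 1/3 followed by 0/3, so P(clear) = (1−p)³ + 3p(1−p)²(1−p)³. If a share s of DLTs is laboratory-only and a fraction d of those is detected, the observed rate is p′ = p[1 − s(1−d)]. With true p = 0.40 and d = 13/27 = 0.48 (pattern X, L = 7, in every participant):
- Full detection: 0.216 + 0.093 = 0.309.
- s = 0.25: p′ = 0.348; P(clear) = 0.400.
- s = 0.50: p′ = 0.296; P(clear) = 0.502.

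At a true rate of 30% the chance goes from 49% to 58–66%; at 50%, from 17% to 26–36%.

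L, the onset distribution, s and p are assumptions; the documents give none of them.

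**5. Where windows stop overlapping.** Visits 7 days apart have disjoint windows only if 2w < 7, that is w ≤ 3. At w = 3 the longest permitted gap is 13 days (for example Day 12 to Day 25); at w = 1, the PK tolerance, it is 9.

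**The case against.** The strongest reply is that the plan already fixes the days: "Assessments must occur on cycle 1, days 1, 8, 15, and 22, on Cycle 2, days 1 and 15" is mandatory wording, Appendix I gives each day its own column, and nothing says that one draw may stand for several. A strict site would draw labs on each. That is a fair reading, but nothing excludes the other one, and a site using the window could point to the sentence that grants it. The two sentences need reconciling in both places.

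Second, participants are seen anyway: weekly ECGs, and PK with CD4/CD8 counts and viral load at about Day 22. This stands against a stronger inference that a reader might draw, namely that compliant sites may replace three visits with one. That would conflict with these provisions unless the general window also covers the ECGs and PK is waived. It does not close the gap in the labs, because neither provision ties blood counts or chemistry to those days; pattern Y keeps the Day 22 visit and has the longer gap.

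Third, short self-resolving events may be uncommon under continuous dosing of a drug with a half-life near 91 hours. An unseen abnormality would also trigger no dose hold, so it might persist until the next panel. This stands as a limit on size, as the 14-day row of the table shows. Continuous AE monitoring (Section 6.1) covers symptomatic events but sets no laboratory frequency.

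**Conclusion.** The concern holds as an unreconciled timing rule that, read literally, permits 14- to 21-day gaps between Cycle 1 safety panels while laboratory DLTs count toward escalation. Some transient, silent laboratory DLTs could be missed; symptomatic ones are unaffected. In the worst-case illustration (7-day events, uniform onset, laboratory share of 25–50%, pattern X in every participant) the chance of clearing a level with a true 40% DLT rate rises from 31% to about 40–50%. For 14-day events, pattern X misses none and pattern Y misses 26%. Even the nominal weekly schedule misses some events shorter than a week.

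A reader might go further and suppose that half of all DLTs go unseen, which would put clearance at 71% (p′ = 0.20: 0.512 + 0.197 = 0.709). The documents do not support that. At 48% detection the laboratory-only share would have to be 0.5/0.52 = 96%; even at 26% detection it would be 0.5/0.74 = 68%. Yet every event listed as likely in Section 7.1 is clinical (such as diarrhea, fatigue and hypertension), platelet decrease is listed as less likely, and neutrophil decrease appears only among events with insufficient evidence of causation.

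One related point: the synopsis applies a duration of more than 5 days to uncomplicated grade 4 neutropenia, whereas Sections 5.2 and 12.1 count any duration. These must be reconciled. A duration criterion could not be verified with panels 14 to 21 days apart.

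**What to change.** In Section 9.2 and Appendix I, limit the ±7-day window to assessments after Cycle 2 Day 1. Give Cycle 1 and Cycle 2 Day 1 a window that cannot overlap between visits (no more than ±3 days), and state that one draw may not count for two scheduled visits.

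In Sections 5.2 and 12.1, require the Day 8, 15, 22 and Cycle 2 Day 1 safety labs, each within its window, before a participant counts as evaluable without a DLT. A participant who has a DLT stays evaluable regardless. Tie the requirement to scheduled panels and not to calendar weeks: Day 8 labs on Day 5 and Day 15 labs on Day 18 are both within ±3 days but leave Days 8–14 without a draw.

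The cost is a few sentences and a schedule footnote, with no added visits. Sites lose some scheduling freedom, and there may be a few more deviations or replaced participants, which matters somewhat at the 1–2 participants per month in Section 12.2. The change does not restore strict weekly sampling, since ±3 days still allows a 13-day gap, but it ends the sharing of draws and the 21-day case.
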